#### Primary Efficacy Endpoint:

#### Secondary Efficacy Endpoints:

1. Average daily TCS during the 2018-2019 Mountain Cedar pollen season.
2. Proportion of days during pollen season for which active patients experience a lower TCS than placebo patients
3. Patient reported pain or discomfort immediately after and 30 minutes post ILIT procedure
4. Patient-reported treatment satisfaction at the end of the study
5. Reduction in allergen-specific serum IgE between the baseline and end-of-study visit

#### Exploratory Endpoints:

1. Use of rescue inhalers by patients with asthma

## 9.2 SAMPLE SIZE DETERMINATION

To determine sample size, the following were assumed:

- Tests will be two-sided and performed at the  $\alpha = 0.05$  significance threshold, as noted in Section 9
  - Study participants will complete the diary assessments (DSS, DMS) to yield a daily TCS on at least 50% of the possible days during the allergy season
  - The difference between the average daily TCS for the placebo group and the ILIT group will 8.0 with an assumption that the standard deviation of the average daily TCS is 9.0 across both groups
  - The randomization will be 1:1
  - Using a priori sample size for multiple linear regression with an effect size 0.50 ( $f^2$ ) for the active treatment group
  - The screen failure rate is estimated to be approximately 12%
- A total of 26 screened patients will be required to enroll a total of 23 subjects into this two-treatment parallel-design study (up to 16 per group), the probability is 80% that the study will detect a treatment difference at a two-sided 0.05 significance level, if the true difference between treatments is a 0.50 effect size under multiple linear regression with two predictors (Soper, D.S. (2018). A-priori Sample Size Calculator for Multiple Regression [Software]. Available from <http://www.danielsoper.com/statcalc>).

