Endpoints:	
Primary Efficacy Endpoint:
 
 
Average daily TCS during the 2018-2019 Mountain Cedar pollen season
 
 
Secondary Efficacy Endpoints:
 
 
Proportion of days during pollen season for which active patients experience a lower TCS than placebo patients
 
Patient reported pain or discomfort immediately after and 30 minutes post ILIT procedure
 
Patient-reported treatment satisfaction at the end of the study
 
Reduction in skin reactivity assessed using allergenic-specific serum IgE testing from pre-treatment to post-treatment (the end-of-study visit)
 
 
Exploratory Endpoints:
 
 
Use of rescue inhalers by patients with stable asthma
 
 
Safety Endpoints:
 
 
Proportion of subjects experiencing a serious, treatment-emergent AE up to 60 minutes after an intranodal injection procedure
 
Proportion of subjects experiencing systemic reactions to ILIT relative to placebo and severity of reactions relative to placebo as assessed by the Total Safety Score (TSS)
 
Proportion of subjects reporting local injection site reactions relative to placebo and severity of local reactions relative to placebo, as assessed by the TSS
 

Study Population:	
This study will include up to 40 screened and 32 enrolled adult patients aged 18 or older with seasonal allergic rhinitis (SAR) and conjunctivitis due to pollen from the conifer Mountain Cedar (Juniperus ashei).

Key Inclusion Criteria:	
 
Both male and female adult patients with a history of SAR with bothersome symptoms due to Mountain Cedar pollinosis confirmed using the Modified Quantitate Test (MQT; defined as a wheal greater than or equal to 3 millimeters larger than the diluent control)a
 
Patients must be willing to provide written, informed consent
 
Patients must be willing and able to comply with study procedures
 
Women of childbearing potential must agree to use an acceptable form of contraception during the trial
 

Key Exclusion Criteria:	
 
Patients less than 18 years of age
 
Clinically-significant chronic sinusitis, as determined by the investigator
 

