## 9 STATISTICAL CONSIDERATIONS

Statistical analysis will be performed by the sponsor-investigator or qualified designee using appropriate statistical analysis software. Analyses requiring significance testing will be two-sided at a 5% significance level, unless otherwise specified. All confidence intervals will be two-sided 95% confidence intervals.

Before unblinding, the programming and testing of the analysis programs and datasets will be completed in accordance with the specifications within the protocol. Assessment tools, including the TSS, TCS, DMS, DSS, NRS-11, and other PROs are attached in Appendix 3.

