5. SAMPLE SIZE CONSIDERATIONS

5.1. Significance Level and Power

To determine sample size, the following were assumed:

Statistical Analysis Plan

- Tests will be two-sided and performed at the $\alpha = 0.05$ significance threshold
 - Study participants will complete the diary assessments (DSS, DMS) to yield a daily TCS on at least 50% of the possible days during the allergy season
 - The difference between the average daily TCS for the placebo group and the ILIT group will 8.0 with an assumption that the standard deviation of the average daily TCS is 9.0 across both groups
 - The randomization will be 1:1
 - Using a priori sample size for multiple linear regression with an effect size 0.50 (f^2) for the active treatment group
 - The screen failure rate is estimated to be approximately 12%
-
- A total of 26 screened patients will be required to enroll a total of 23 subjects into this two-treatment parallel-design study (up to 16 per group), the probability is 80% that the study will detect a treatment difference at a two-sided 0.05 significance level, if the true difference between treatments is a 0.50 effect size under multiple linear regression with two predictors (Soper, D.S. (2018). A-priori Sample Size Calculator for Multiple Regression [Software]. Available from <http://www.danielsoper.com/statcalc>).

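### The 80% power claim uses f² = 0.50, but the plan's own 8.0-point difference and SD of 9.0 give f² ≈ 0.20, so power is about 53% at 23 patients and 68% at 32

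*Protocol*

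**What the plan says.** Protocol 9.2 lists its sample-size assumptions together, and SAP 5.1 repeats them:

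- **Treatment difference:** "The difference between the average daily TCS for the placebo group and the ILIT group will 8.0".
- **Variability:** "the standard deviation of the average daily TCS is 9.0 across both groups".
- **Effect size:** 0.50, labelled f² and assigned to the active treatment group, in a multiple regression.
- **Allocation and screen failure:** 1:1, and about 12%.

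The conclusion drawn is "A total of 26 screened patients will be required to enroll a total of 23 subjects into this two-treatment parallel-design study", with up to 16 per group. The power claim is that "the probability is 80% that the study will detect a treatment difference at a two-sided 0.05 significance level". The only condition attached to that claim is the regression effect size: "if the true difference between treatments is a 0.50 effect size under multiple linear regression with two predictors". Protocol section 9 sets the level: "Analyses requiring significance testing will be two-sided at a 5% significance level, unless otherwise specified".

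Other sections give a different enrolment number. The synopsis says "This study will include up to 40 screened and 32 enrolled adult patients", and protocol 5.4 calls 32 the target sample size.

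The planned primary test also differs between the documents. Protocol 9.4.2 uses a general linear model with treatment and daily pollen count. SAP 9.1 uses ANOVA or Kruskal-Wallis on group average TCS in the per-protocol set and names no second predictor.

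**The concern.** A difference with its SD already fixes the effect size, so a separately stated f² must agree with it. Here it does not, and neither document derives 0.50 from 8.0 and 9.0. SAP 5.2 reports that earlier studies found TCS differences of 1 to 8 units. The 8.0 is therefore already the top of that range, and f² = 0.50 implies an effect well beyond it.

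The test used for sizing is a second problem. An overall test of two predictors asks whether treatment or pollen count explains TCS, whereas the power claim is about detecting a treatment difference.

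What is at stake is how the result is read. TCS is the labelled primary efficacy endpoint, and under SAP 6.7 its test gates the secondary endpoints. A non-significant result would carry the label of an 80%-powered study when, at 23 patients, the chance of detecting the assumed effect is close to even.

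**Working it through.** **Inputs.** Difference 8.0, SD 9.0, f² = 0.50, two predictors, 1:1 allocation, two-sided α = 0.05, N = 23 enrolled and 26 screened, 12% screen failure (protocol 9.2 and SAP 5.1); 32 enrolled and up to 40 screened (synopsis); target of 32 (protocol 5.4).

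**1. Reproduce the plan's figure.** Overall F test of a regression with two predictors: df1 = 2, df2 = N − 3, noncentrality λ = f²·N.

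- N = 22: λ = 0.50 × 22 = 11.0, power 78.8%.
- N = 23: λ = 0.50 × 23 = 11.5, power 81.0%.

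So 23 is the smallest N reaching 80% with f² = 0.50 on the 2-df test. The 1-df treatment test at f² = 0.50 would need only 18. Screening: 23/0.88 = 26.1, which matches the stated 26 after rounding down.

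**2. Effect size implied by the plan's own difference and SD.**

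- d = 8.0/9.0 = 0.889.
- With 1:1 allocation, f = d/2 = 0.444 and f² = d²/4 = 0.198.

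**3. What f² = 0.50 would require.**

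- d = 2√0.50 = 1.414.
- At SD 9.0, the difference is 1.414 × 9.0 = 12.7 points.
- At a difference of 8.0, the SD is 8.0/1.414 = 5.7.

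The documents state neither value.

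**4. Power at 8.0 points and SD 9.0**, with no variance explained by the second predictor:

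| Test | N = 23 | N = 32 | N for 80% |
|---|---|---|---|
| Two-sample t (11 vs 12; 16 vs 16) | 52.9% | 68.2% | 42 |
| 1-df treatment F, two-predictor model | 52.7% | 68.1% | 42 |
| 2-df overall F (the plan's method) | 40.7% | 56.1% | 52 |

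The t-test noncentrality is d·√(n₁n₂/(n₁+n₂)), which is 0.889 × √(132/23) = 2.13 at N = 23 and 0.889 × √8 = 2.51 at N = 32.

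**5. Difference detectable with 80% power** (two-sample t, SD 9.0): d = 1.226, or 11.0 points, at 23; d = 1.024, or 9.2 points, at 32. Both exceed the assumed 8.0.

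**6. Alternative readings, all at N = 23.**

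- SD 9.0 is the total SD including the treatment difference: f² = 0.1975/(1 − 0.1975) = 0.246, power 62%.
- 0.50 was meant as f: f² = 0.25, power 63%.
- The second predictor explains a share r² of the residual variance, so f² = 0.198/(1 − r²). The documents give no r², so these values are assumptions:

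| r² | N = 23 | N = 32 |
|---|---|---|
| 10% | 57% | 73% |
| 30% | 68% | 83% |
| 50% | 82% | 93% |

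To reach 80%, r² would have to be about 25% at N = 32 and nearly half at N = 23.

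**The case against.** The strongest reply is that 32, not 23, is the working target, so the fair comparison is 68% against 80%. Section 9.2 itself allows up to 16 per group, and a required minimum of 23 can sit beside a ceiling of 32. This stands in part: the enrolment numbers are a matter of tidying rather than an error of equal weight. But the 80% claim is attached to 23, and 32 still falls short.

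A second reply is that covariate adjustment would recover power. Protocol 9.4.2 includes pollen count, and SAP 6.3 names baseline serum IgE as an explanatory covariate. It is right that 53% and 68% depend on assuming no variance explained, and the corrected text should say so. The documents give no figure for any gain, however. Pollen count is an unlikely source: SAP 6.2 says all patients were enrolled at the Austin site, so they share one pollen series, which can hardly explain differences between patients in season averages. SAP 9.1 names no covariate in the primary test.

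A third reply is that this is an exploratory phase 2 proof-of-concept study in which efficacy comes second to safety, and that correcting the text changes no patient, test or estimate. That justifies a small trial. It does not justify an explicit 80% statement that its own inputs contradict.

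How 0.50 arose is not documented. A value of f (0.444 here) entered in place of f² is possible, but that is inference and nothing rests on it.

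**Conclusion.** The concern holds. The sample-size sections of both documents contain two incompatible effect sizes, f² = 0.198 and f² = 0.50, and the 80% claim depends on the one that does not follow from the stated difference and SD. The 2-df test used for sizing also does not address the treatment effect.

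For the assumed 8.0 points, the shortfall is about 27 percentage points at 23 evaluable patients (80 − 53) and 12 at 32 (80 − 68). These figures take SD 9.0 as the within-group SD, a two-sided 5% treatment test, no variance explained by a covariate and no loss of patients from the analysis. Section 9.2 allows only for screen failures, while SAP 9.1 analyses the per-protocol set, so exclusions would lower power further. The other readings of the SD and of 0.50 reach at most 63% at 23. Only a covariate effect that the plan does not state would restore 80%.

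**What to change.** In protocol 9.2 and SAP 5.1:

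- Replace f² = 0.50 with f² = 0.198 (d = 0.89), and show that it comes from 8.0/9.0 under 1:1 allocation.
- Base power on the 1-df treatment test instead of the overall two-predictor test.
- State the resulting figures for 8.0 points: about 68% power with 32 evaluable and 53% with 23. Give the differences detectable with 80% power: 9.2 and 11.0 points.
- Say that these figures assume no variance explained by a covariate and make no allowance for per-protocol exclusions.
- Use one enrolment target, 32, in the synopsis, protocol 5.4, protocol 9.2 and SAP 5.1.

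The cost is wording only. Enrolment and the planned tests stay as they are. The stated power becomes less favourable.

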## 9.3 POPULATIONS FOR ANALYSES

- Intent-to-Treat (ITT) Analysis Dataset: will include all randomized participants and be used for subject listings and demographics tables.
- Modified Intention-to-Treat (MITT) Analysis Dataset: will include all participants who received at least one (1) study intervention and completed at least one (1) complete daily e-diary assessment and be used for production of efficacy tables, subject listings, and demographics tables.
- Safety Analysis Dataset: will include all participants who took received at least one (1) dose of study intervention regardless of whether they provided any diary data and will be used for safety tables and tolerability tables.
- Per-Protocol (PP) Analysis Dataset: will include the subset of participants in the MITT data set who received three study treatment injections and completed at least 50% of e-diary responses during the allergy season (follow-up period), and has no other major protocol violations, and will be used for production of supplementary efficacy tables and analyses.
- Additional datasets for sub-population will include the adjusted ITT, MITT, Safety Dataset, and PP dataset for the subset of patients with asthma at baseline.

## 9.4 STATISTICAL ANALYSES

### 9.4.1 GENERAL APPROACH

This study is committed to the use of valid and reliable statistical methods in accordance with ICH E9, Statistical Principles for Clinical Trials for exploratory clinical trials. Thus, while this trial employs pre-specified objectives and tests of pre-defined hypotheses, this trial may require a more flexible approach to analysis in response to accumulating results. Statistical methods using appropriate transformations and non-parametric testing will be applied. Tests of underlying assumptions of specified tests will be performed. If required assumptions are not met, alternative analytic tests will be applied, as appropriate, and the reasons for selection will be reported in the publication.

---

#### 9.4.2 ANALYSIS OF THE PRIMARY EFFICACY ENDPOINT(S)

The efficacy analysis will be secondary to the relative assessment of safety between groups. For efficacy, the primary analysis will be based on the difference of average daily total combined score (TCS), which is the sum of the daily symptom score (DSS) and daily medication score (DMS) between groups analyzed using a general linear model with daily pollen count at the study site and treatment as fixed effects, adjusting for different error variation for each treatment group. An exploratory adjustment using allergic asthma at baseline as a co-variate will also be performed. Additional nonparametric analysis with the Wilcoxon rank sum test may be conducted on the DMS if the data are not normally distributed and heavily weighted by zero values. There will be no imputation for missing data.

---

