9. EFFICACY ANALYSIS

9.1 Primary Efficacy Analysis

Objective: To evaluate the efficacy of ILIT relative to placebo during the 2018-2019 Texas Mountain Cedar allergy season as assessed by the daily total combined score (TCS), a composite of the Daily Symptoms Score (DSS) and Daily Medication Score (DMS).

Endpoint: Average daily TCS during the 2018-2019 Mountain Cedar pollen season

Population: The per protocol dataset, which includes participants who received three study treatment injections and completed at least 50% of expected electronic diary responses during the allergy season, with no major protocol violations.

Analysis Period: The analysis period will be peak mountain cedar pollen season in the local area, defined as the period when the first cedar pollen count was above 100 ppm to the last date pollen was above 100 ppm followed by more than five (5) consecutive days with a count below 100 ppm.

Statistical Testing Method and Considerations: The TCS is a repeated measure, but statistical comparisons were between group average TCS scores during peak season. Between group comparisons will be made using either ANOVA, a parametric test, if the underlying data distribution supports use of parametric testing, otherwise the comparison will be made using a non-parametric test, the Kruskal-Wallis test, based on rank order.

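### Neither document fixes the patient as the unit of the primary TCS analysis; on a day-level reading, diary days would count as independent observations

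*Protocol*

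**What the plan says.** Protocol 9.4.2 bases the primary efficacy analysis on the between-group difference in average daily TCS, "analyzed using a general linear model with daily pollen count at the study site and treatment as fixed effects". It allows the error variance to differ by arm and rules out imputation. It names no patient term, repeated-measures covariance or clustered standard error.

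SAP 9.1 gives a different method for the same endpoint: "The TCS is a repeated measure, but statistical comparisons were between group average TCS scores during peak season". The test is ANOVA if the distribution allows it, otherwise Kruskal-Wallis. SAP section 1 says that SAP definitions prevail for analysis and that discrepancies with the protocol will be described. SAP 9.1 does not describe this change.

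Four other SAP sections bear on the unit:

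- SAP 7.4 derives TCS for each patient on each diary day and defines no per-patient season mean.
- SAP 9.2 uses the group average TCS to mean the average of a group on a single day.
- SAP 9.3 (Other Efficacy Analyses) still refers to a multiple regression model for efficacy, and SAP 5.1 still sizes the trial "under multiple linear regression with two predictors".
- SAP 6.3 mentions a linear mixed model, but only as one option for examining baseline IgE as a covariate.

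**The concern.** The pollen count in the protocol model changes from day to day. According to SAP 6.2 all patients came from one site, so on any given day the count is the same for everyone. The natural way to use it is with one row per patient per day. With only fixed effects in the model, the many days from one patient then enter as if they came from different patients. Letting the error variance differ between arms does not touch the correlation among one patient's days.

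The SAP acknowledges the repeated measures but does not close the gap. Its comparison of group averages could be run on patient season means, on patient-days, or on daily group means. Only the first has the patient as the unit.

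The choice matters beyond one p-value. SAP 6.7 makes the single primary test the gate to the ordered secondary endpoints, so an error there would carry down the sequence.

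**Working it through.** **Inputs from the documents.** Two-sided alpha 0.05 (Protocol 9: "Analyses requiring significance testing will be two-sided at a 5% significance level"); 80% power, f² = 0.50, two predictors, 23 enrolled, and SD 9.0 for the average daily TCS (Protocol 9.2, SAP 5.1).

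**Inputs assumed.** The documents give neither the number of diary days per patient (m) nor the correlation between two days of the same patient (ICC). I take m = 80 as the main case. The diary is planned for about December to March, and Protocol 2.2 reports 78 season days in an earlier US intralymphatic trial. The ICC is varied.

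**Step 1: reproduce the plan's sample size.** The regression F test has u = 2 numerator and N − 3 denominator degrees of freedom, with noncentrality f² × N. At N = 22 the power is 0.788. At N = 23 the noncentrality is 0.50 × 23 = 11.5 and the power is 0.810. The stated 23 reproduces, with one row per subject.

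**Step 2: which ICC values are possible.** TCS runs from 0 to 38 (six symptoms × 3 = 18; medication 6 + 6 + 8 = 20), so the SD of a daily score cannot exceed about 38/2 = 19. If the between-patient SD is 9, the daily SD is about 9/√ICC: 28 at ICC 0.1, 20 at 0.2, 14 at 0.4, 12 at 0.6 and 10 at 0.8. With that SD, ICC values below (9/19)² = 0.22 are impossible. I use 0.4 to 0.8.

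**Step 3: error rate if patient-days are the rows.** The design effect is DE = 1 + (m − 1) × ICC, and the actual two-sided alpha is 2 × [1 − Φ(1.96/√DE)]. With m = 80:

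| ICC | DE | 1.96/√DE | Actual alpha |
|---|---|---|---|
| 0.4 | 1 + 79 × 0.4 = 32.6 | 0.343 | 0.73 |
| 0.6 | 1 + 79 × 0.6 = 48.4 | 0.282 | 0.78 |
| 0.8 | 1 + 79 × 0.8 = 64.2 | 0.245 | 0.81 |

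Simulation of 2,000 null trials per setting, 12 against 11 patients and 80 days, with daily TCS regressed on treatment and a shared pollen curve, gave 74%, 79% and 81%.

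**Step 4: sensitivity to days, variance by arm, and unit.** A second simulation, again with 2,000 null trials of 12 against 11 patients, included the arm-specific variance. At m = 60 and ICC 0.5 it gave:

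- Patient-days with pollen and arm-specific variance: 0.727. The formula gives DE = 1 + 59 × 0.5 = 30.5 and alpha 0.723; 23 × 60 = 1,380 rows carry the information of 1,380/30.5 ≈ 45.
- ANOVA on daily group means: 0.714.
- One mean per patient, Welch test: 0.051.

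Across m = 30 to 90 and ICC 0.3 to 0.7, patient-days gave 0.53 to 0.82, daily group means 0.43 to 0.86, and one mean per patient 0.04 to 0.05. A season of only 14 days at ICC 0.3 still gives 0.38 by the formula.

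**The case against.** The strongest reply is that neither document tells the analyst to use patient-days, and much of the text points the other way. The endpoint is an average daily TCS over the season. The SD of 9.0 is for that average. The sample size is in subjects and reproduces with one row per subject. The SAP's remark on repeated measures can be read as saying that the days are averaged out before the arms are compared, and SAP 9.2 works by day because its endpoint is a percentage of days. All of this stands, and it makes one value per patient the probable intention.

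Nor does a pollen term force patient-day rows. The protocol planned three treatment cities, and single-site enrolment is reported only in the SAP. A pollen value averaged by site, or over each patient's completed diary days, could serve as a patient-level covariate. That stands too, but the protocol names a daily count and describes no averaging, so the day-level reading remains the natural one.

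The SAP's precedence removes the pollen model from the operative analysis, and the error rates for that model should be read with this in mind. It does not settle the unit, which SAP 9.1 leaves open. Protocol 9.4.1 promises checks of test assumptions and alternative tests where they fail, but that does not name the unit either.

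A reader might infer that the trial's primary p-value is invalid as planned. The documents do not support that: a valid patient-level analysis is within what they allow.

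**Conclusion.** The concern holds as an unresolved unit of analysis, together with a protocol model that ignores within-patient correlation on its natural reading. It is not a demonstrated invalid test. If patient-days are the rows, a nominal 5% test would reject a true null about 73% to 81% of the time, given the assumed 80 days and ICC of 0.4 to 0.8; daily group means as the unit do similar damage. One season mean per patient gives about 5%. The exact inflation depends on assumed values, but it is large at every setting tried. Exploratory phase 2 status does not remove the issue, because the SAP keeps a single primary hypothesis test.

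**What to change.** State in SAP 9.1 that the patient is the unit: compute one season-average TCS per patient over the defined season and compare arms on those values. Add that derivation to SAP 7.4. Alternatively, specify a linear mixed model on daily TCS with treatment, daily pollen count and a random patient effect, a stated within-patient correlation structure, and small-sample degrees of freedom.

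Put the same method in Protocol 9.4.2 and SAP 9.3 (Other Efficacy Analyses), record the change of method as SAP section 1 requires, and describe the sample-size model in Protocol 9.2 and SAP 5.1 consistently with it.

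No new data are needed. If a per-patient mean was always intended, one sentence settles the unit. The downside is standard errors wider than those from patient-days, which is the correct price. Aligning the sample-size text will also raise a separate question: a difference of 8.0 with SD 9.0 corresponds to f² = (8/9)²/4 ≈ 0.20, not 0.50.
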